#### Stopping Rules for patient accrual at initial presentation

Based on the expectation that the relapse rate after radiation therapy alone will be 25% or less, RFS will be evaluated in each of the two subgroups of previously untreated patients and accrual stopped in RFS is < 70% after the first 15, 30, or 45 patients have been followed for a minimum of 2-years. Assuming that 70% of the relapsing patients will fail within 5 years, computer simulations indicate that this stopping rule will terminate patient accrual in both the gastric and non-gastric arms of the trial with a probability of 1% if the relapse rate is 25% with a 17% probability if the relapse rate is 50%, and with a probability of 60% if the relapse rate is 75%.

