2)  $\geq 50\%$  increase in greatest diameter of any previously identified node greater than 1 cm its short axis or in the SPD of more than one node.

**Progressive disease** (PR, nonresponders) – 1)  $\geq 50\%$  increase from nadir in the SPD of any previously identified abnormal node for PRs or nonresponders. 2) Appearance of any new lesion during or at the end of therapy.

b. Response Assessment

Response is assessed on the basis of clinical radiologic, and pathologic (i.e, bone marrow) criteria. CT scans remain the standard for evaluation of nodal disease. Thoracic, abdominal, and pelvic CT scans are recommended even if those areas were not initially involved because of the unpredictable pattern of recurrence.

A bone marrow aspirate and biopsy should only be performed to confirm a CR if it is clinically indicated by new abnormalities in the peripheral blood counts or blood smear.

c. Response durations are measured from the time of response (not the beginning of treatment) until there is evidence of progressive disease. Progression free survival will be measured from protocol entry.

8.3 Frequency of Response Determination: All lesions must be measured at baseline and then as per section 7.4

8.4 Survival Durations: The survival of patients will be measured from entry into protocol.

8.5 All toxicities encountered during the study will be evaluated according to the grading system (0-4) in Appendix C. Duration and treatment will be recorded. Life-threatening toxicities should be reported immediately to the study chairman who in turn must notify the IRB. Should this occur, it will mandate closure of the protocol to patient entry for investigation as to the reasons for this and a decision can be taken as to whether the protocol can remain open or should be closed.

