## 11.0 Statistical Considerations and Stopping Rules

This is a trial to estimate the relapse-free survival rate (RFS) of patients with gastric and non-gastric MALT lymphoma treated with radiation therapy alone. Patient accrual is expected to be 10 – 15 per year for gastric and 5 – 10 per year for non-gastric MALT lymphoma at initial presentation. Accrual of less than 5 patients per year for either gastric or non-gastric MALT lymphoma is expected for presentation upon failure of other treatment modalities. The patient accrual and outcome analyses will be done separately in the following 4 groups: Gastric vs non-gastric MALT at initial presentation vs upon failure to other treatment(s).

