#### Accrual goals

The accrual goals for the patients at initial presentation are 40 for gastric and 35 for non-gastric MALT lymphoma. Based on the expectation that the relapse rate after radiation therapy alone will be 25% and that 70% of the relapsing patients will fail within 5 years, these numbers will provide a 95% confidence bound of +/- 5.9% for estimating the 2-year RFS. This calculation assumes that RFS follows an exponential distribution and we will follow all patients for at least 2 years.

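### The 45-patient stopping look exceeds both accrual goals, and at the planned steady rates the 30-patient look falls after accrual ends, so the stated 1/17/60% stopping probabilities do not describe the design

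*Combined protocol and SAP*

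**What the plan says.** All of this is in section 11.0 unless noted.

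- **Rule.** For patients at initial presentation, "RFS will be evaluated in each of the two subgroups of previously untreated patients", with "accrual stopped in RFS is < 70% after the first 15, 30, or 45 patients have been followed for a minimum of 2-years".
- **Goals.** "The accrual goals for the patients at initial presentation are 40 for gastric and 35 for non-gastric MALT lymphoma".
- **Rates.** "Patient accrual is expected to be 10 – 15 per year for gastric and 5 – 10 per year for non-gastric MALT lymphoma". The same paragraph keeps accrual and outcome analysis separate for the four patient groups.
- **Stated performance.** The figures rest on simulation under a timing assumption: "Assuming that 70% of the relapsing patients will fail within 5 years, computer simulations indicate" the results. The event they describe is worded as follows: "this stopping rule will terminate patient accrual in both the gastric and non-gastric arms of the trial". Its chance is put at 1% for a 25% relapse rate; the other two figures are given as "with a 17% probability if the relapse rate is 50%, and with a probability of 60% if the relapse rate is 75" (percent).
- **Endpoint.** Section 8.2 defines relapsed disease and says "Progression free survival will be measured from protocol entry". The accrual-goals paragraph names 2-year RFS as the quantity to be estimated. Nothing says whether a stopping look counts relapses within 2 years or all relapses to date.
- **Previously treated patients.** Section 2.1 extends the same stopping rule to them. Section 11.0 defers any analysis of their data until both initial-presentation goals have been reached.

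**The concern.** A look at 45 patients cannot take place in an arm that closes at 40 or 35, and pooling the arms is ruled out by the separate analyses. Each look also waits for 2 years of follow-up on its last patient. If enrolment continues meanwhile, a look can come when there is no accrual left to stop.

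This is the plan's only pre-specified efficacy stopping rule, and section 11.0 says there is no stopping rule for toxicity. Readers are told how likely the rule is to end accrual if radiation alone performs poorly. If those probabilities credit looks that cannot act, they describe a different trial.

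**Working it through.** **1. Reachability.** 45 > 40 and 45 > 35. No model is needed.

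**2. Timing.** Assume steady accrual at the section 11.0 rates, no pause and no loss to follow-up. The look at k patients falls at k/rate + 2 years; accrual ends at goal/rate; the number enrolled at the first look is min(goal, 15 + 2 × rate).

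| Arm, rate per year | Look 15 (yr) | Look 30 (yr) | Accrual ends (yr) | Enrolled at look 15 |
|---|---|---|---|---|
| Gastric, 10 | 3.5 | 5.0 | 4.0 | 35 of 40 |
| Gastric, 12.5 | 3.2 | 4.4 | 3.2 | 40 of 40 |
| Gastric, 15 | 3.0 | 4.0 | 2.67 | 40 of 40 |
| Non-gastric, 5 | 5.0 | 8.0 | 7.0 | 25 of 35 |
| Non-gastric, 10 | 3.5 | 5.0 | 3.5 | 35 of 35 |

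A look precedes the end of accrual only if rate < (goal − k)/2.

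- Look 30: below (40 − 30)/2 = 5 per year gastric, or (35 − 30)/2 = 2.5 per year non-gastric. Both are outside the planned ranges.
- Look 15: below (40 − 15)/2 = 12.5 per year gastric, or (35 − 15)/2 = 10 per year non-gastric.

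**3. Reproducing 1/17/60%.** The plan does not state the simulation model. The following one is inferred: a share R relapses, 70% of those within 5 years, with exponential times, and only relapses within 2 years count.

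- Rate = −ln(0.3)/5 = 0.2408 per year.
- 2-year relapse probability = R × (1 − e^(−2 × 0.2408)) = R × 0.382, which is 0.0955, 0.1911 and 0.2866 for R = 25%, 50% and 75%.
- RFS below 70% means more than 4.5, 9 or 13.5 relapses, so at least 5 of 15, 10 of 30 or 14 of 45.

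Exact cumulative probability of stopping one arm:

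| Looks counted | R = 25% | R = 50% | R = 75% |
|---|---|---|---|
| Stated in plan | 1% | 17% | 60% |
| 15, 30, 45 | 1.07% | 16.5% | 59.2% |
| 15, 30 | 1.06% | 15.5% | 51.7% |
| 15 only | 1.05% | 14.2% | 43.8% |

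Within this model the stated figures are matched at all three relapse rates only with all three looks. The second row of results is what would apply if accrual paused at 15 and at 30 patients. The third applies under steady accrual where the first look is in time.

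**4. Both arms or each arm.** Joint stopping of two independent arms on this model would be 0.0107² = 0.01%, 0.1648² = 2.7% and 0.592² = 35.0%. The stated figures fit one arm.

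**5. Sensitivity to how relapses are counted.** If all follow-up to the look counts, patient i has 2 + (15 − i)/rate years. On the same relapse model the first look alone gives:

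| Arm, rates at which look 15 is in time | R = 25% | R = 50% | R = 75% |
|---|---|---|---|
| Gastric, 10–12 per year | 2.3–2.5% | 25–27% | 64–67% |
| Non-gastric, 5–9 per year | 2.7–4.4% | 29–40% | 69–81% |

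**6. Sensitivity to uneven accrual.** With Poisson accrual (an assumption), look 15 comes before accrual ends with probability 47% at 12.5 per year and 16% at 15 per year (gastric), and 47% at 10 per year (non-gastric). For look 30 the probability is at most 2.9% anywhere in the planned ranges.

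**The case against.** Four counter-arguments deserve an answer.

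**The model is a back-fit.** The accrual-goals paragraph assumes that RFS itself is exponential. With 0.7 × 25% = 17.5% relapse at 5 years, 2-year RFS is 0.825^0.4 = 0.926, and 75 patients give 1.96 × √(0.926 × 0.074/75) = 5.9 points, as stated there; the inferred model gives 6.65. Yet that simple exponential, with 2-year relapses and three looks, yields 0.4/8.1/44.6%, not 1/17/60%. A reader might infer that the stated probabilities can arise only by counting the two later looks. That does not follow. The simple exponential with all follow-up counted and the first look alone gives 1.2/18.2/58.5% at 10 per year. That match does not persist across rates (2.8/31.9/76.8% at 5 per year), and it is not the three-look rule in the text, but it rules out an unqualified claim.

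**The 60% may not be too high.** A reader might infer that the plan overstates its protection. The 2-year requirement is a minimum, so longer follow-up may count. On that reading the first look alone exceeds 60% where it is in time, and the 1% and 17% figures rise too. The direction is not established.

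**The rule is not wholly inert at fast accrual.** A reader might infer that no look can act at the upper rates. That holds only for perfectly even enrolment; with random accrual the first look is sometimes in time.

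**Little turns on it.** This is an estimation trial and the RFS estimate is unaffected. No pause is stated, but none is excluded, and with pauses two looks give 1.1/15.5/51.7%. This stands as a limit on severity. It does not rescue the 45-patient look or the stated probabilities.

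**Conclusion.** The rule is wrong as written and should be corrected. That the 45-patient look cannot occur follows from the goals alone. The lateness of the 30-patient look rests on the planned rates and on there being no pause, and it survives random accrual almost entirely. The 15-patient look is reliably in time only at the slower planned rates.

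The 1/17/60% figures therefore do not describe the rule that the trial can operate. If only 2-year relapses count, the figure at 75% relapse falls from about 59% to 44% (first look) or 52% (two looks with pauses); the 25% figure hardly moves, and the 50% figure falls by at most about 2 points from the reproduced 16.5%. If all follow-up counts, all three figures rise at the first look. The size and sign of the error cannot be settled from the documents.

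The practical stakes are modest. Under steady accrual a stop at the first look spares at most 40 − 35 = 5 gastric patients (at 10 per year) or 35 − 25 = 10 non-gastric patients (at 5 per year).

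**What to change.** 1. Delete the 45-patient look, or replace the set with looks that fit goals of 40 and 35.
2. State whether RFS at a look means 2-year RFS or all relapses to date, and whether accrual pauses while follow-up matures.
3. Rerun the simulation under one stated accrual and relapse model. Report the stopping probabilities per arm, counting only looks that can occur before accrual ends, and say that accrual stops in each arm rather than in both.
4. Secondary: reconcile section 2.1 with the section 11.0 paragraph on patients who failed other treatments, so that those groups have one stated rule.

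The cost is an amendment of two short paragraphs and one sentence of the rationale, plus a simulation rerun. No extra patients, visits or data are needed. The restated probabilities may look less favourable. An accrual pause is optional; each one would lengthen accrual by up to about 2 years.

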### 2.0 Background

2.1 Rationale- MALT lymphoma is a relatively recently described entity which is also known as extranodal marginal zone lymphoma (1)(2)(3)(4). It was initially recognized in gastrointestinal tract with the majority arising from the stomach. Nowadays, however, about 30 to 40% of the MALT lymphomas are thought to be of non-gastrointestinal origin according to the M.D. Anderson Cancer Center lymphoma data base and others (5). Though MALT lymphoma constitute about 7 to 8%(6) of non-Hodgkin's lymphoma, prospective clinical trials are scarce and optimal treatments still remain to be defined. It is generally considered to be a low grade lymphoma at early state (7)(8) having a very favorable prognosis even after localized treatments such as radiation therapy or surgical resection alone (9)(10). Most of the data on the treatments of MALT lymphoma come from experiences in gastric MALT lymphoma (11)(12)(13). There have been multiple retrospective series suggestive of favorable outcome for these patients. However, the first report on a prospective clinical trial in managing Ann Arbor stage 1 and 2 gastric MALT lymphoma with radiation therapy alone was published in 1998 and has been recently updated (14)(15). Twenty nine patients were treated with a median dose of 30 Gy (range 22.5 to 43.5) delivered at 1.5 Gy per fraction to the stomach and adjacent lymph nodes. At a median follow-up of 30 months, 94 % remain disease free. Non-gastric MALT lymphomas (16) (3)(5) have been reported in sites such as bowel (17) lung (18), breast (19)(20), skin (21), thyroid gland (22), bladder (23)(24), liver (25) dura (26)(27), esophagus (28) ocular adnexa (29)(30) along with other head and neck series limited by a small number of patients treated in a variety of different ways including any combination of chemotherapy, radiation therapy and surgery, thus yielding no significant insights into the optimal treatment except for the impression that most of them are very localized disease with favorable prognosis probably comparable to that of gastric MALT lymphoma (7). Therefore, we propose to prospectively study the efficacy and toxicity of radiation treatment for patients with stage 1 and 2 non-gastric MALT lymphoma as well as to verify the Memorial Sloan-Kettering Cancer Center data on gastric MALT lymphoma. Of note, a recent publication from the Non-Hodgkin's Lymphoma Classification Project reported an overall failure free survival of about 70% or higher if the International Prognostic Index is less than 4 in their retrospective analysis of 72 patients with stage 1 to 4 MALT lymphoma (33). Zinzani et al reported 5 year treatment failure rate of 70% for their review of 47 patients with stage 1 and 2 non-gastric MALT lymphoma(16). Based on the failure free survival curves presented in these studies, we believe it is a very reasonable hypothesis to test 75% or higher relapse free survival at 5 years with the majority of the relapses occurring within the first 5 years in our group of patients.

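### The RFS < 70% stopping rule names no time point; on the 2-year scale that reproduces its printed probabilities it is a weak check on the 25% relapse expectation, and two of its three looks come too late to stop accrual

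*Combined protocol and SAP*

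**What the plan says.** The stopping rule for patients at initial presentation (section 11.0) opens with its premise: "Based on the expectation that the relapse rate after radiation therapy alone will be 25% or less". RFS is then evaluated separately in the gastric and non-gastric subgroups, with "accrual stopped in RFS is < 70% after the first 15, 30, or 45 patients" reach at least 2 years of follow-up. No time point is attached to the RFS that is compared with 70%, and no reason is given for choosing 70%.

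The simulation input is stated: "Assuming that 70% of the relapsing patients will fail within 5 years". The printed results are stopping probabilities of 1%, 17% and 60% for relapse rates of 25%, 50% and 75%.

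The neighbouring Accrual goals text sets 40 gastric and 35 non-gastric patients, takes 2-year RFS as the quantity to be estimated, and adds: "This calculation assumes that RFS follows an exponential distribution and we will follow all patients for at least 2 years". The opening paragraph of section 11.0 expects 10–15 gastric and 5–10 non-gastric patients per year at initial presentation. Section 2.1 states the clinical hypothesis on another time scale: "it is a very reasonable hypothesis to test 75% or higher relapse free survival at 5 years".

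**The concern.** A cut-off of 70% means different things at different times. The plan's own assumptions place most relapses after 2 years, so 70% at 2 years is a far worse outcome than 70% at 5 years. If the comparison is made at 2 years, the rule tolerates relapse rates well above the one it is introduced to monitor.

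The second issue is timing. The rule acts by stopping accrual, but each look must wait until its patients have 2 years of follow-up. A look that falls after the last patient is enrolled cannot stop anything, and its contribution to the printed probabilities is not real protection.

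This is the only numerical stopping rule in the plan, since section 11.0 states that there is none for toxicity. Those who approve or oversee the trial would rely on the 1%, 17% and 60% figures.

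**Working it through.** **Inputs.** Eventual relapse rate r = 0.25, 0.50 or 0.75; 70% of relapses within 5 years; exponential times; cut-off RFS < 70%; looks at 15, 30 and 45 patients; goals of 40 and 35; accrual of 10–15 and 5–10 per year (all from section 11.0).

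**Step 1: true 2-year RFS.** Let a fraction r relapse, with exponential times and 70% of them by 5 years. The share of relapses that occurs by 2 years is 1 − 0.3^(2/5) = 1 − 0.618 = 0.382. Then S(2) = 1 − 0.382r and S(5) = 1 − 0.7r.

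| Eventual relapse | S(2) | S(5) |
|---|---|---|
| 25% | 90.4% | 82.5% |
| 50% | 80.9% | 65.0% |
| 75% | 71.3% | 47.5% |

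**Step 2: reproduce the plan's figures.** RFS < 70% means at least 5 relapses in 15, 10 in 30 or 14 in 45 (21 of 30 relapse-free is exactly 70% and does not stop). An exact sequential binomial on 2-year status, in one arm, gives these cumulative stopping probabilities:

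| Looks | 25% relapse | 50% relapse | 75% relapse |
|---|---|---|---|
| 15, 30 and 45 | 1.1% | 16.5% | 59.2% |
| 15 and 30 | 1.1% | 15.5% | 51.7% |
| 15 only | 1.1% | 14.2% | 43.8% |
| Printed in the plan | 1% | 17% | 60% |

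The first row matches. Other readings do not:

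- The crude relapse-free proportion at the look date, at 7.5–12.5 patients per year, gives about 1–5%, 42–74% and 96–100%.
- Kaplan-Meier RFS at last follow-up gives 18–40%, 79–95% and 99–100%.
- Reading the relapse rate as the 5-year rate gives 97.6% at 75% relapse.
- One exponential curve for all patients, with S(5) = 1 − 0.7r and 2-year status, gives 0.4%, 8% and 45%.
- Both independent arms stopping would have probability 0.592² = 35% at 75% relapse, so the 60% is a one-arm figure, although the sentence refers to both arms.

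**Step 3: where the boundary sits.** Setting 1 − 0.382r = 0.70 gives r = 0.30/0.382 = 0.785. The corresponding 5-year RFS is 1 − 0.7 × 0.785 = 45%. Under one constant hazard for all patients it would be 0.70^2.5 = 41%.

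**Step 4: when the looks fall.** A look at n patients occurs at n/rate + 2 years; accrual ends at goal/rate.

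| Subgroup, rate per year | Accrual ends (years) | Look at 15 | Look at 30 |
|---|---|---|---|
| Gastric, 10 | 4.0 | 3.5 | 5.0 |
| Gastric, 15 | 2.7 | 3.0 | 4.0 |
| Non-gastric, 5 | 7.0 | 5.0 | 8.0 |
| Non-gastric, 10 | 3.5 | 3.5 | 5.0 |

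The 45-patient look exceeds both goals. The 30-patient look precedes the end of accrual only if 30/rate + 2 < goal/rate, that is below 5 per year (gastric) or 2.5 per year (non-gastric), both under the planned rates. The 15-patient look can act below 12.5 per year (gastric) or 10 per year (non-gastric).

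**Step 5: an illustrative cut-off.** RFS < 80% means 11 or fewer relapse-free of 15, or 23 or fewer of 30.

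| Looks | 25% relapse | 50% relapse | 75% relapse |
|---|---|---|---|
| 15 only | 4.8% | 31.9% | 66.3% |
| 15 and 30 | 5.7% | 44.1% | 84.3% |

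The chance that at least one of two independent arms stops wrongly at 25% relapse is 1 − 0.952² = 9.4% or 1 − 0.943² = 11.1%.

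**The case against.** The best defence is disclosure. The plan prints its stopping probabilities, so any reader can see that the rule seldom stops at 50% relapse and misses 40% of cases at 75%. Section 11.0 describes an estimation trial, and section 2.1 a disease with a favourable outlook. A rule that almost never stops a treatment performing as expected is a defensible choice, and a tighter cut-off costs more false stops. This stands as far as the choice of cut-off goes: 80% is one possible trade-off, not a correction. It does not answer the missing time point, or the fact that the disclosed figures include looks that cannot stop accrual.

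Two stronger readings are tempting.

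- A reader might infer that 70% was set from the 5-year hypothesis ("75% or higher relapse free survival at 5 years") and then carried to 2 years by mistake. The two figures are 5 points apart, but nothing in the protocol links them.
- A reader might also infer that the rule works backwards, with more data making a stop less likely. The cumulative probability rises with each look: 14.2%, 15.5%, 16.5% at 50% relapse and 43.8%, 51.7%, 59.2% at 75%. Taken singly, the looks do decline at 50% relapse (14.2%, 4.7%, 3.7%), but at 75% they are not monotone (43.8%, 34.9%, 41.3%).

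Nor is the rule inoperative. At 75% relapse the boundary is only 1.3 points below the true 2-year RFS, and sampling variation still triggers a stop in 44–59% of trials, depending on the looks counted.

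**Conclusion.** The concern holds in this form: the time point is unstated, the 2-year reading is the only one examined that fits the printed figures, and on that reading the rule is a weak check on the 25% expectation. With the two looks inside the accrual goals, an arm with 50% eventual relapse (5-year RFS 65%) crosses the boundary 15.5% of the time, and one with 75% (5-year RFS 47.5%) crosses it 51.7% of the time. With the single look that can precede the end of accrual, the figures are 14.2% and 43.8%, against a printed 17% and 60%. At 15 gastric patients per year even that look comes after accrual has ended (3.0 v 2.7 years), and at 10 non-gastric patients per year it coincides with the end.

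This rests on four assumptions: relapse rate means eventual relapse, as the plan's wording implies; looks are made per subgroup, as stated; accrual is steady at the planned rates and is not paused to await follow-up, since no pause is described; and all patients have known 2-year status. Under one exponential curve for everyone the rule is weaker still: 0.4%, 7.9% and 39.4% with looks at 15 and 30.

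**What to change.** In the stopping-rule text of section 11.0:

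1. State the boundary as the Kaplan-Meier estimate of 2-year RFS, evaluated in each arm.
2. Remove the 45-patient look, and the 30-patient look unless the plan provides for it to take place before accrual ends. State the accrual rate above which the 15-patient look also comes too late.
3. Restate the simulated probabilities per arm for the looks that remain, and correct the wording that attaches them to both arms.
4. Either say plainly that < 70% at 2 years guards only against about 78% or more eventual relapse, or recalibrate the cut-off on the 2-year scale and give the reason for the value chosen.

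Items 1 to 3 and the first option in item 4 need only rewording and a re-run of the simulation. Recalibrating has a price: at < 80%, the chance of stopping an arm that meets the 25% expectation rises from about 1% to about 5–6%, or about 9–11% for at least one of two arms. Much of the gain shown for 80% with two looks (84.3% at 75% relapse) is unavailable unless the 30-patient look can act; with the 15-patient look alone it is 66.3%.

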## 10.0 Data and Protocol Management

10.1 Protocol Compliance: The attending physician must see each patient prior to the start of irradiation and at each follow-up visit post-treatment. All required interim and pretreatment data should be available and the physician must make a designation as to tumor response and toxicity grade.

10.2 Data Entry: Data must be entered into the Protocol Data Management system before therapy can be given. A brief explanation for required but missing data should be recorded as a comment.

10.3 Accuracy of Data Collection: The study chairman will be the final arbiter of response or toxicity should be a difference of opinion exist.

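### The accrual stopping rule waits for the scheduled 15-patient look even when five early relapses have already put 2-year RFS below 70%

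*Combined protocol and SAP*

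**What the plan says.** Section 11.0, under the stopping rules for patients at initial presentation, applies the rule by arm: "RFS will be evaluated in each of the two subgroups of previously untreated patients", with "accrual stopped in RFS is < 70% after the first 15, 30, or 45 patients have been followed for a minimum of 2-years". No clause stops accrual earlier once the result is certain, and none suspends it while follow-up matures. The section does not say at what time point RFS is read.

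The stated chance of stopping is 1%, 17% and 60% for relapse rates of 25%, 50% and 75%, from simulations made "Assuming that 70% of the relapsing patients will fail within 5 years".

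Expected accrual is 10-15 per year for gastric disease and "5 – 10 per year for non-gastric MALT lymphoma at initial presentation". The targets are: "The accrual goals for the patients at initial presentation are 40 for gastric and 35 for non-gastric MALT lymphoma".

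**The concern.** For a fixed cohort, a threshold on 2-year RFS amounts to a relapse count. Once that count is reached, completing follow-up on the remaining patients cannot bring RFS back to the threshold. The rule nevertheless holds the decision until the fifteenth patient has completed 2 years. Patients can therefore keep entering an arm that has already failed the plan's own criterion. At the faster planned accrual rates the wait lasts until the arm is full, and the rule then has nothing left to stop.

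**Working it through.** **Inputs from Section 11.0.** Threshold 70%; looks at 15, 30 and 45 patients with 2 years of follow-up; 70% of relapsing patients fail by 5 years; accrual 10-15 (gastric) and 5-10 (non-gastric) per year; goals 40 and 35.

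**Assumptions.** Exponential relapse times among relapsing patients, evenly spaced entry, no loss to follow-up, and accrual open until the look or the goal.

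**1. The plan's own figures.** Rate = -ln(0.3)/5 = 0.241 per year, so 1 - 0.3^0.4 = 38.2% of eventual relapses occur by 2 years. The 2-year relapse probabilities are 0.25 × 38.2% = 9.6%, 0.50 × 38.2% = 19.1% and 0.75 × 38.2% = 28.7%. Stopping at 5 or more of 15, 10 or more of 30, or 14 or more of 45 gives 1.1%, 16.5% and 59.3% per arm by simulation, against the stated 1%, 17% and 60%. This supports the 2-year reading. The first look alone gives 1.1%, 14.2% and 43.8% (exact binomial).

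**2. The threshold as a count.**
- First 15: 5 relapses give 10/15 = 66.7% (stop); 4 give 11/15 = 73.3% (continue).
- First 30: 10 relapses give 20/30 = 66.7% (stop); 9 give 21/30 = 70.0% (continue).

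Censoring cannot rescue an arm that has reached the count, because a Kaplan-Meier estimate never exceeds (n - d)/n.

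**3. Calendar.** The look at n patients falls at n/rate + 2 years, and the goal is reached at goal/rate.

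| Arm, rate | 15-patient look (y) | 30-patient look (y) | Goal reached (y) |
|---|---|---|---|
| Gastric 10/y | 3.5 | 5.0 | 4.0 |
| Gastric 15/y | 3.0 | 4.0 | 2.67 |
| Non-gastric 5/y | 5.0 | 8.0 | 7.0 |
| Non-gastric 10/y | 3.5 | 5.0 | 3.5 |

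**4. Arms that cross at 15** (100,000 simulated arms per setting, 75% relapse). Enrolment is capped at the goal. The last column assumes each relapse is found 0-12 months late (uniform).

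| Arm, rate | Median lead of 5th relapse (y) | Mean enrolled at look | Mean enrolled at 5th relapse | Difference | Difference with delay |
|---|---|---|---|---|---|
| Gastric 10/y | 1.21 | 35 | 23 | 12 | 7 |
| Gastric 15/y | 1.01 | 40 | 29 | 11 | 4 |
| Non-gastric 5/y | 1.65 | 25 | 16 | 9 | 6 |
| Non-gastric 10/y | 1.21 | 35 | 23 | 12 | 7 |

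At 50% relapse the enrolment pairs are 35 vs 24, 40 vs 31, 25 vs 17 and 35 vs 24, with median leads of 0.9-1.5 years. Across both relapse rates, the delay cuts the median lead to about 0.4-1.1 years and the difference to about 3-7 patients.

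**5. Chance that accrual stops before the goal, 75% relapse.** Running counts here means 5 of 15 or 10 of 30.

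| Arm, rate | As written | Running counts | Running counts, 0-12 month delay |
|---|---|---|---|
| Gastric 10/y | 44% | 48% | 45% |
| Gastric 15/y | 0% | 42% | 27% |
| Non-gastric 5/y | 44% | 49% | 47% |
| Non-gastric 10/y | 0% | 45% | 39% |

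**The case against.** **The 30-patient look.** A reader might infer that the same year of needless enrolment arises there. It does not: the first table shows the goal is reached before that look at every documented rate. Enrolment avoided by acting on the tenth relapse averages 0-3 patients, and the 10-of-30 count adds only a few percentage points of actual stopping.

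**No statistical gain from waiting.** This is also tempting, but it is true only of the stop decision. Section 11.0 describes a trial to estimate RFS, and extra patients add precision. Against that, the plan itself chose to close an arm below 70%.

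**Counts are not a full substitute for the look.** With 2 of 15 patients censored before any event and 4 relapses, RFS is 9/13 = 69.2%, which stops under the plan although the count is not reached. In the other direction, Section 4.2.3 removes from analysis patients given chemotherapy for a concurrent malignancy. If one of five relapsed patients is removed and not replaced, RFS is 10/14 = 71.4%. Section 10.3 also lets a disputed response be overruled. These points stand, and the fix must allow for them.

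**The endpoint is inferred.** Section 11.0 does not say whether RFS at a look uses 2-year data or all follow-up, or whether deaths count. If relapses at any time before the look count, the median lead is shorter, about 0.6-1.4 years.

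**The size is conditional.** The enrolment figures describe crossing arms only. Averaged over all arms, the saving is about 0.1 patients at the expected 25% relapse, 1.1-1.6 at 50% (14.2% × 7.8 to 11.3) and 3.8-5.4 at 75% (43.8% × 8.6 to 12.4). Detection may also be slow: Section 7.3 repeats abnormal imaging and endoscopy at 3 months and then yearly, and the note after 7.4 allows fewer visits.

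**Conclusion.** The point holds for the 15-patient look. On 2-year RFS, the fifth qualifying relapse settles the decision a median of 0.9-1.7 years early at 50-75% relapse, or 0.4-1.1 years with a 0-12 month detection delay. About 8-12 patients per crossing arm enter in that interval, or 3-7 with the delay. At the plan's expected 25% relapse, only about 1% of arms cross, so the matter counts mainly if radiation alone does worse than hoped.

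The more consequential result is at the upper accrual rates. There the rule as written stops no enrolment, while acting on the counts would close about 42% (gastric, 15 per year) and 45% (non-gastric, 10 per year) of arms before the goal at 75% relapse, or 27% and 39% with the delay.

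These figures rest on the plan's relapse-timing assumption, even accrual, complete follow-up and the inferred 2-year endpoint. Fixed looks are a legitimate design. This is a cheap improvement that should be made, and it does not invalidate the rule.

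**What to change.** In Section 11.0:
- Keep the scheduled RFS looks and the 70% threshold.
- State that the rule uses 2-year RFS, and whether deaths count as events.
- Add that accrual to an untreated arm stops as soon as 5 of the first 15, or 10 of the first 30, analysable patients have a confirmed relapse within 2 years of entry, without waiting for the others to complete 2 years.
- Apply the Section 4.2.3 analysis exclusion and the Section 10.3 arbitration before a relapse is counted.
- State that if the count is not reached, the RFS estimate at the scheduled look still decides. This keeps the protection against censoring.

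If the sponsor changes the look sizes or the threshold, the counts should be derived again in the same way.

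The cost is a few sentences and a running tally per arm. Section 10.1 already requires the source data, since at each visit "the physician must make a designation as to tumor response and toxicity grade". No visits or patients are added. The price is a less precise RFS estimate in an arm that the plan's own rule would close.
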